
Analysis for Primary Ischemic Endpoint
	
The analysis for the primary ischemic endpoint will be performed on the PP cohort. The primary objective is to determine if ticagrelor monotherapy is non-inferior to ticagrelor plus aspirin for the primary ischemic endpoint (all-cause death, non-fatal myocardial infarction, or stroke). Event rates will be estimated at one year and Kaplan-Meier curves will be plotted for the time from randomization to the first occurrence of confirmed all-cause death, non-fatal myocardial infarction, or stroke or by treatment group. A test of non-inferiority at the one-sided 0.025 level will be performed. . . . Assuming an event rate of 8.0% in the control group, a sample size of 8200 will yield 80% power to exclude an absolute non-inferiority margin of 1.6%. If the upper limit of the 95% CI for the point estimate of the absolute risk difference between groups is less than or equal to 1.6% then the criteria for non-inferiority will be met. This non-inferiority margin translates to a relative risk of 20% assuming the observed event rate equals 8.0% in the control arm.

Statistical Methods
	
Unless otherwise stated, all hypothesis tests will be performed using two-sided tests at the 5% significance level. Continuous variables will be summarized using descriptive statistics including means and standard deviations if normally distributed or median with interquartile ranges for skewed distributions. Discrete variables will be summarized using absolute and relative frequencies.

Sample Size Parameters
	
A cumulative bleeding rate of 4.5% is anticipated between time of randomization and 1 year. Assuming a 2% loss to follow-up and non-compliance / cross-over rate of 4%, the current trial will require 8200 subjects to detect a relative reduction in bleeding of 28% with ticagrelor monotherapy with 80% power and a Type I error of 0.05. It is anticipated that approximately 8% - 10% of enrolled subjects will not be eligible for randomization and therefore 9000 subjects will be enrolled at the time of PCI.

[figure not shown]

TABLE OF CONTENTS	PAGE
TITLE PAGE	1
PROTOCOL SYNOPSIS	2
TABLE OF CONTENTS	7
PROTOCOL SIGNATURE PAGE	11
LIST OF ABBREVIATIONS	12
1. INTRODUCTION	13
1.1 Research hypothesis.....	14
1.2 Rationale for conducting this study	14
1.3 Benefit/risk and ethical assessment.....	15
2. STUDY OBJECTIVES	15
2.1 Primary objective	15
2.2 Secondary objective	16
2.3 Exploratory objectives	16

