1.1 Research hypothesis

The overall hypothesis of the current study is that three months post-PCI of dual antiplatelet therapy with aspirin and ticagrelor, continued monotherapy with ticagrelor alone versus ticagrelor plus aspirin for an additional year will be superior with respect to bleeding and non-inferior with respect to ischemic events in high-risk patients undergoing elective or urgent PCI.

This hypothesis will be tested in the following two specific aims:

Aim 1: To determine the impact of ticagrelor alone versus ticagrelor plus aspirin in reducing clinically relevant bleeding among high-risk patients who had PCI.
	
Hypothesis 1: A DAPT strategy of ticagrelor + ASA for 3 months followed by ticagrelor alone for an additional 12 months will be superior to ticagrelor plus aspirin with respect to clinically relevant bleeding (BARC \geq 2) in high-risk patients undergoing PCI.

Aim 2: To determine the impact of ticagrelor alone versus ticagrelor plus aspirin in reducing ischemic adverse events at one year among high-risk patients undergoing PCI
	
Hypothesis 2: A DAPT strategy of ticagrelor + ASA for 3 months followed by ticagrelor alone for an additional 12 months will be non-inferior to ticagrelor plus aspirin for with respect to ischemic adverse events at 1 year in high-risk patients undergoing PCI.

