12.1.2 Safety analysis set

Analyses for the primary ischemic endpoint will be performed on the PP cohort. A secondary analysis for the primary ischemic endpoint will be performed in the ITT cohort.

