12.2 Methods of statistical analyses

Unless otherwise stated, all hypothesis tests will be performed using two-sided tests at the 5% significance level. Continuous variables will be summarized using descriptive statistics including means and standard deviations if normally distributed or median with interquartile ranges for skewed distributions. Discrete variables will be summarized using absolute and relative frequencies.

Demographic and baseline characteristics will be summarized by randomized treatment group and for all randomized subjects combined. Baseline characteristics that will define subgroups of interest for the efficacy and safety analyses are:

- Age group (< 65, >= 65 years)
- Race (Caucasian, non-Caucasian)
- Gender (Male, Female)
- Geographic Region (US, non-US)
- Diabetes Mellitus (yes, no)
- Chronic Kidney Disease (yes, no)

- CAD Presentation (Stable, Unstable)
- PCI Status (Elective, Urgent)
- Stent length implanted (< 30 mm, >=30 mm)
- BMI (above median, below median)
- History of Prior MI (yes, no)
- Multivessel disease (yes, no)

Censoring: Subjects not experiencing any endpoint will be censored at time of death, last contact date (for subjects who withdraw consent or are lost to follow-up) or 365 days after randomization, whichever comes first.

Analysis for the Primary Bleeding Endpoint: This analysis will be performed on the ITT population. The primary objective is to determine if ticagrelor monotherapy is superior to ticagrelor plus aspirin for the primary efficacy endpoint (BARC Types 2, 3 or 5 bleeding). The null hypothesis for this analysis is that the HR for the experimental group (H_0) = 1. The alternative hypothesis is that the HR for the experimental group (H_A) \neq 1. A test of superiority at the two-sided 0.05 level will be performed using a Cox proportional hazard model that includes treatment group as a covariate. A point estimate and two-sided 95% CI for the relative risk as measured by the hazard ratio will be calculated based on the Cox proportional hazards model. Event rates will be estimated at one year and Kaplan-Meier curves will be plotted for the time from randomization to the first occurrence of confirmed BARC Type 2, 3 or 5 bleeding by treatment group. This analysis will be repeated in the PP cohort to support the primary results.

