Analysis for the Primary Ischemic Endpoint: The analysis for the primary ischemic endpoint will be performed on the PP cohort. The primary objective is to determine if ticagrelor monotherapy is non-inferior to ticagrelor plus aspirin for the primary safety endpoint (all-cause death, non-fatal myocardial infarction, or stroke). A test of non-inferiority at the one-sided 0.025 level will be performed. Event rates will be estimated at one year and Kaplan-Meier curves will be plotted for the time from randomization to the first occurrence of confirmed all-cause death, non-fatal myocardial infarction, or stroke or by treatment group. Assuming an event rate of 8.0% in the control group, a sample size of 8200 will yield 80% to exclude a non-inferiority margin of 1.6%. If the upper limit of the 95% CI for the point estimate of the absolute risk difference is less than or equal to 1.6% then the criteria for non-inferiority will be met. This non-inferiority margin translates to a relative risk of 20% assuming the observed event rate equals 8.0% in the control arm.

Subgroup Analysis One year event rates for the primary efficacy and safety endpoints will be calculated in all subgroups described in section 12.2. Stratum-specific HRs and corresponding 95% CI will be calculated for each subgroup using a Cox proportional hazards

model. Formal interaction testing will be performed using the subgroup X treatment allocation as an additional term in the Cox model.

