12.3 Determination of sample size

Power calculations are based on a superiority comparison for the primary efficacy endpoint of clinically relevant bleeding (BARC Types 2, 3 or 5) at 1 year from randomization (15 months after enrollment). Based on bleeding rates as shown in Table 3, a cumulative bleeding rate of 4.5% is anticipated between time of randomization and 1 year. This estimate is more conservative than rates shown in Table 3 as subjects sustaining a major hemorrhagic event in the first 3 months after PCI will not be randomized. Assuming a 2% loss to follow-up and non-compliance / cross-over rate of 4%, the current trial will require 8200 subjects to detect a relative reduction in bleeding of 28% with ticagrelor monotherapy with 80% power with a Type I error of 0.05. It is anticipated that approximately 8% - 10% of enrolled subjects will not be eligible for randomization and therefore 9000 subjects will be enrolled. Additional sample size estimates are provided in Table 4 assuming different control bleeding rates and risk reductions. References for the sample size estimates include Lakatos 1988, Biometrics volume 44 pages 229-241; and Lakatos 2002, Statistics in Medicine, Volume 21 pages 1969-1989.

Assuming a 1 year ischemic adverse event rate of 8% the current study will have 80% power to exclude a non-inferiority margin of 1.6% (upper limit of 95% CI for absolute risk difference).

Table 2 Bleeding Rates/Effect Sizes for Primary Endpoint Power Calculations

Basis for Proposed Bleeding Event Rates in TWILIGHT Power Calculations			
Study	Study Type	Time Point	BARC \geq 2 Rate
DAPT	RCT	18 months	~ 4.2%
PARIS (unpublished data)	Registry		
Age > 65	Registry	1 year	8.6%
Diabetes Mellitus (on insulin)	Registry	1 year	8.3%
Diabetes Mellitus (orals)			6.3%
Renal disease	Registry	1 year	13.2%
Vranckx et al., EHJ 2013	Post-hoc (TRACER)	500 days	14%
ADAPT-DES			
CrCl < 60 (Baber et al, TCT 2013)	Registry	1 year	10.0%
Rao et al., JACC Int 2013	NCDR CathPCI	In-hospital (women)	8.5%
Basis for Proposed Effect Size in TWILIGHT Power Calculations			

Study	Study Type	Comparators	Relative Bleeding Increase
Baigent et al., Lancet 2009	Pooled Data from Randomized trials	ASA vs. placebo/control	50% (1° prevention) 170% (2° prevention)
WOEST, Lancet 2013	RCT	ASA vs. placebo	~ 60%
CAPRIE, Lancet 1996	RCT	ASA vs. clopidogrel	~35% (GI hemorrhage)
Physician Health Study, NEJM 1989	RCT	ASA vs. Placebo	~35%

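### Does the ischemic non-inferiority analysis need a prespecified overall hazard ratio because the 1.6-point margin equals 20% only at an 8.0% control rate?

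*Combined protocol and SAP*

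**What the plan says.** The ischemic endpoint is the time to first death from any cause, non-fatal myocardial infarction or stroke (section 11.1.3). Section 12.2 sets the test: "A test of non-inferiority at the one-sided 0.025 level will be performed". The synopsis states the rule in terms of the upper 95% limit: if that limit for the "absolute risk difference between groups is less than or equal to 1.6% then the criteria for non-inferiority will be met". Section 12.2 has the same rule, and section 12.3 ties the power statement to the same absolute limit: "Assuming a 1 year ischemic adverse event rate of 8% the current study will have 80% power". No relative margin and no second criterion appear anywhere.

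Both the synopsis and section 12.2 then give a relative reading with its condition attached: "This non-inferiority margin translates to a relative risk of 20% assuming the observed event rate equals 8.0% in the control arm".

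The estimates named differ by endpoint:

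- **Bleeding** (section 12.2): "A point estimate and two-sided 95% CI for the relative risk as measured by the hazard ratio will be calculated" from the Cox model.
- **Ischemic, overall** (section 12.2): one-year event rates, Kaplan-Meier curves and the risk difference with its 95% interval.
- **Ischemic, by subgroup** (section 12.2, which covers both primary endpoints): "Stratum-specific HRs and corresponding 95% CI will be calculated for each subgroup using a Cox proportional hazards" model.
- **Ischemic, second population** (section 12.1.2): "A secondary analysis for the primary ischemic endpoint will be performed in the ITT cohort", with no estimate named.

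**The concern.** Section 1.1 expects monotherapy to be "superior with respect to bleeding and non-inferior with respect to ischemic events in high-risk patients", so the ischemic result carries half of the study's claim. A fixed absolute margin loosens in relative terms as the control rate falls. If fewer events occur than planned, a pass may be compatible with a relative excess in death, infarction or stroke well above 20%. Taken literally, the plan would then offer only one overall relative figure for this endpoint, the planning value of 20%, which may not fit the observed rate.

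The contrast with bleeding sharpens the point. An overall hazard ratio is promised there, and stratum hazard ratios are promised for both endpoints, but no overall ischemic hazard ratio is. A reader could fear that the choice of relative summary would be made after the data were seen.

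**Working it through.** **Inputs.** Margin 1.6 points, control rate 8.0%, one-sided level 0.025 and 8,200 randomized (synopsis; section 12.2). Assumptions: 1:1 allocation, so n = 4,100 per arm; complete follow-up; normal approximation; control rates other than 8%.

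**1. The plan's own figure.** 1.6 / 8.0 = 0.20, a relative risk of 1.20. The stated 20% is reproduced exactly.

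**2. The margin at other control rates.** Relative excess = 1.6 / rate.

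| Control rate | 10% | 8% | 7% | 6% | 5% | 4% |
|---|---|---|---|---|---|---|
| 1.6 points as a relative excess | 16% | 20% | 23% | 27% | 32% | 40% |

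The margin is looser than 20% below 8% and stricter above it.

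**3. What a barely passing result shows on the ratio scale.** With p0 and p1 the control and monotherapy event proportions:

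- Upper limit of the risk difference = (p1 − p0) + 1.96 × √[p1(1 − p1)/n + p0(1 − p0)/n]
- Upper limit of the relative risk = (p1/p0) × exp{1.96 × √[(1 − p0)/(n·p0) + (1 − p1)/(n·p1)]}

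At 8%, control events are 0.08 × 4,100 = 328. The largest monotherapy count that passes is 344: the difference is 16/4,100 = 0.39 points, the standard error 0.606 points, and the upper limit 0.39 + 1.96 × 0.606 = 1.58 points. The relative risk is 344/328 = 1.049, the standard error of its logarithm 0.0739, and its upper limit 1.049 × exp(1.96 × 0.0739) = 1.212.

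| Control rate | Events, monotherapy vs control | Upper relative-risk limit | 1 + 1.6/rate |
|---|---|---|---|
| 10% | 422 vs 410 | 1.171 | 1.160 |
| 9% | 383 vs 369 | 1.189 | 1.178 |
| 8% | 344 vs 328 | 1.212 | 1.200 |
| 7% | 306 vs 287 | 1.245 | 1.229 |
| 6% | 268 vs 246 | 1.288 | 1.267 |
| 5% | 230 vs 205 | 1.348 | 1.320 |
| 4% | 193 vs 164 | 1.443 | 1.400 |

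The converted margin is therefore not a bound on a ratio interval at any of these rates. A bare pass at 8.0% does not exclude 1.20, while at 9% and 10% it does. The 20% is a translation of the margin, as the plan presents it, and not a promise about a confidence limit.

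**4. Results inside the margin.** Equal event counts pass at every rate from 4% to 8%: the upper risk-difference limits are 0.85, 0.94, 1.03, 1.10 and 1.17 points. The matching upper relative-risk limits are 1.24, 1.21, 1.19, 1.17 and 1.16. With truly equal arms, simulation gives the share of passing results that also exclude 1.20 as 41%, 52%, 64%, 76% and 90%. A pass and exclusion of 20% are different events, and only one of them is the plan's criterion.

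**5. The decision itself.** The null hypothesis is a true difference of 1.6 points. Comparing the upper 95% limit with 1.6 points has a one-sided error of about 2.5% whatever the control rate. If the true relative excess were 20%, the chance of passing would be 2.5% at a control rate of 8%, 11% at 6%, 22% at 5% and 42% at 4%. The last three are not false passes: the true differences there are 1.2, 1.0 and 0.8 points, all inside the stated margin.

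**The case for a change.** The strongest case for acting is that the plan prints a relative figure, makes it conditional on an observed rate, and does not say what will be reported if that rate differs. It names an overall hazard ratio where it wants one. The remedy would cost one Cox model per population on data already collected and would leave the margin, rule and power untouched. At an assumed 5% rate, a bare pass has an upper relative-risk limit of 1.35, and readers should see that.

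Much of this stands. The overall ischemic hazard ratio is not written down, the contrast with bleeding is real, and its interval would inform readers.

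It does not amount to a defect. The plan never adopts a relative margin, so measuring passes against 1.20 applies a criterion it did not set. The 8.0% condition is stated openly, which warns readers against carrying the 20% to another rate. The endpoint is defined as a time to first event, and the plan already commits to Cox models for it by subgroup and for interaction, so the overall model is a natural companion. The named one-year rates give a crude ratio, and event counts with arm sizes give an approximate interval, apart from censoring (2% loss to follow-up is assumed in section 12.3). A rule tying every relative statement to the hazard-ratio limit would go further and restrict interpretation; nothing here requires it.

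**Conclusion.** No change follows. The plan leaves one reporting detail unwritten, the overall ischemic hazard ratio with its 95% interval in the per-protocol and intention-to-treat populations, and analysts can be expected to supply it. The absolute criterion is legitimate and used consistently, the 20% conversion is correct at the rate the plan names, and neither the type I error nor the conclusion depends on the missing line. A sponsor who wishes to add it may do so as a courtesy to readers.

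The size of the effect is the drift of the relative reading from 20% at an 8% control rate to 32% at 5% and 40% at 4%. Those lower rates are illustrative. The confidence limits also assume 4,100 per arm with complete follow-up; the per-protocol set would be smaller and its ratio intervals somewhat wider. The stated 80% power is a separate matter on which this conclusion does not rest: with equal true rates of 8%, the normal approximation gives about 76% at 8,200.

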12.3 Determination of sample size

Power calculations are based on a superiority comparison for the primary efficacy endpoint of clinically relevant bleeding (BARC Types 2, 3 or 5) at 1 year from randomization (15 months after enrollment). Based on bleeding rates as shown in Table 3, a cumulative bleeding rate of 4.5% is anticipated between time of randomization and 1 year. This estimate is more conservative than rates shown in Table 3 as subjects sustaining a major hemorrhagic event in the first 3 months after PCI will not be randomized. Assuming a 2% loss to follow-up and non-compliance / cross-over rate of 4%, the current trial will require 8200 subjects to detect a relative reduction in bleeding of 28% with ticagrelor monotherapy with 80% power with a Type I error of 0.05. It is anticipated that approximately 8% - 10% of enrolled subjects will not be eligible for randomization and therefore 9000 subjects will be enrolled. Additional sample size estimates are provided in Table 4 assuming different control bleeding rates and risk reductions. References for the sample size estimates include Lakatos 1988, Biometrics volume 44 pages 229-241; and Lakatos 2002, Statistics in Medicine, Volume 21 pages 1969-1989.

Assuming a 1 year ischemic adverse event rate of 8% the current study will have 80% power to exclude a non-inferiority margin of 1.6% (upper limit of 95% CI for absolute risk difference).

Table 2 Bleeding Rates/Effect Sizes for Primary Endpoint Power Calculations

Basis for Proposed Bleeding Event Rates in TWILIGHT Power Calculations			
Study	Study Type	Time Point	BARC \geq 2 Rate
DAPT	RCT	18 months	~ 4.2%
PARIS (unpublished data)	Registry		
Age > 65	Registry	1 year	8.6%
Diabetes Mellitus (on insulin)	Registry	1 year	8.3%
Diabetes Mellitus (orals)			6.3%
Renal disease	Registry	1 year	13.2%
Vranckx et al., EHJ 2013	Post-hoc (TRACER)	500 days	14%
ADAPT-DES			
CrCl < 60 (Baber et al, TCT 2013)	Registry	1 year	10.0%
Rao et al., JACC Int 2013	NCDR CathPCI	In-hospital (women)	8.5%
Basis for Proposed Effect Size in TWILIGHT Power Calculations			

Study	Study Type	Comparators	Relative Bleeding Increase
Baigent et al., Lancet 2009	Pooled Data from Randomized trials	ASA vs. placebo/control	50% (1° prevention) 170% (2° prevention)
WOEST, Lancet 2013	RCT	ASA vs. placebo	~ 60%
CAPRIE, Lancet 1996	RCT	ASA vs. clopidogrel	~35% (GI hemorrhage)
Physician Health Study, NEJM 1989	RCT	ASA vs. Placebo	~35%
De Berardis et al., JAMA 2012	Cohort study	ASA vs. No ASA	55%
Seshasai et al., Archives Int Med 2012	Meta-analysis of 9 RCTs	ASA vs. Placebo	~31%
HOT Trial, Lancet 1998	RCT	ASA vs. Placebo	~ 80%

Table 3 Power and Sample Size Scenarios for Primary Superiority Endpoint of BARC ≥ 2 Bleeding

Control Bleeding Rate	Relative Risk Reduction	Total Randomized Sample Size	Total Sample Size (Enrolled + Randomized) with 8% loss after enrollment*	Total Sample Size (Enrolled + Randomized) with 10% loss after enrollment*
5%	30%	6400	7000	7111
5%	28%	7400	8040	8222
5%	26%	8030	9800	10000
4.5%	30%	7090	7706	7900
4.5%	28%	8200	8913	9111
4.5%	26%	9700	10500	10800
4.0%	30%	8000	8700	8888
4.0%	28%	9300	10100	10333
4.0%	26%	10900	11800	12111

We anticipate that ~10% of enrolled subjects will not be eligible or lost for randomization. Power calculations assume 2% loss to follow-up and 4% cross-over/non-compliance.

12.4 Data and safety monitoring board

The TWILIGHT study will be conducted under the auspices of an independent Data and Safety Monitoring Board (DSMB), whose activities will be described in a DSMB charter. DSMB members will not have primary affiliation with the study sponsor, the EDC supplier or

the principal investigator of the trial. Members of the Board will be determined prior to study enrollment.

The DSMB will review data and determine reporting and stopping rules as specified in the DSMB charter. The DSMB members will review safety data while maintaining the scientific integrity of the trial. The data to be reviewed will consist of adjudicated and non-adjudicated MACE, Bleeding, and other Serious Adverse Events and their incidence, in order to identify potential safety issues. Based on the safety data, the DSMB may recommend modifications to the protocol, suspension or termination of the trial, and advise the Executive Committee.

Members of the DSMB will meet or conference with steering group members before the trial starts to review the protocol, to determine the meeting schedule, the logistics of reporting the safety data and the stopping rules. Frequency of meetings can change during the study and will be determined by the DSMB and its charter.

All adverse events will be reported to the DSMB and reviewed on an on-going basis throughout the subject enrollment and follow-up period as specified in the DSMB charter to ensure the safety of subjects enrolled in this trial. The DSMB may request additional information as needed. Based on safety data, the DSMB may recommend that the Executive Committee modify or discontinue the trial. All final decisions, regarding trial modifications, however, rest with the Executive Committee.

13. IMPORTANT MEDICAL PROCEDURES TO BE FOLLOWED BY THE INVESTIGATOR

13.1 Overdose

If an overdose on the study drug occurs in the course of the study, then investigators or other site personnel inform appropriate the ARC **within one day**, i.e., immediately but no later than **the end of the next business day** of when he or she becomes aware of it.

The ARC will work with the investigator to ensure that all relevant information is provided to the ARC.

